**Implementation and Evaluation of a Diabetes Prevention
Clinical Pathway in Primary Care**

NCT05265312

Date: 7/11/2023

Introduction

Abstract and Background:

Prediabetes is a significant public health problem affecting 88 million U.S. adults. Evidence suggests that the vast majority of people with prediabetes are unaware that they have this condition and many are not receiving appropriate care for prediabetes, including referral to evidence-based programs like the Diabetes Prevention Programs. In our retrospective cohort study of patients with prediabetes from Johns Hopkins Health Systems, we found that the rates of prediabetes clinical care activities are low. In our qualitative studies, we found that primary care physician (PCP) barriers include low knowledge about Diabetes Prevention Programs and misperceptions of insurance coverage of these programs and inadequate clinical staff to address prediabetes. Common patient barriers to taking action to prevent diabetes include lack of motivation, time and resources.

Primary Hypothesis: We hypothesize that the clinical pathway will result in increased clinician screening and intervention and improve patient engagement in diabetes prevention. We will compare results from the intervention clinic compared to a control clinic. If successful, we plan to implement and test the effectiveness of this clinical pathway across the entire health system.

Purpose of the Study Protocol: As described above, we have conducted several studies to understand current practices in prediabetes care across the Johns Hopkins Health Systems. In our retrospective cohort study of patients with prediabetes from Johns Hopkins, we found that the rates of prediabetes clinical care activities are low. Within 12 months, 63.4% had repeat glycemic testing, yet only 10.4% had coded diagnoses of prediabetes, 1.0% were referred for nutrition services, and 5.4% were prescribed metformin. We were unable to evaluate uptake of Diabetes Prevention Programs (DPPs) since a referral order was not in place until recently. In our qualitative studies, we found that clinician barriers include low knowledge about DPPs and misperceptions of insurance coverage of these programs and inadequate clinical staff to address prediabetes. Common patient barriers to taking action to prevent diabetes include lack of motivation, time and resources.

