This is a pre-/post-evaluation of a diabetes prevention clinical pathway that will be implemented over a 12-month period at the intervention clinic. Eligible patients include those on the prediabetes registry who are seen in the control and intervention clinics during the study period. Their first visit with the PCP will be considered V0 (initial data collection) and data will be collected retrospectively (12 months prior to V0) and prospectively at that visit and subsequent primary care visits (V1, V2, V3, etc.) during the 12-month intervention period (see Figure).

The diabetes prevention clinical pathway will focus on the following steps: 1) Screen/test-testing of eligible patients for prediabetes/diabetes, 2) Education- PCPs will be encouraged to take an online learning module and in-person group training on prediabetes management, and patients with prediabetes will receive a handout about prediabetes prior to their upcoming PCP visit, 3) Action- PCPs will use a shared decision-making guide and treatment algorithm to discuss options with patients at their visit, 4) Referral- patients may be referred to DPPs and/or medical nutrition therapy (MNT), and 5) Treat- patients will be scheduled for a follow-up visit within 3-9 months with their PCP or care team (NP) to continue addressing prediabetes.

Group 1 Intervention clinic patients

PCPs in the intervention clinic will be invited and encouraged to attend the 1-hour clinician training session at the beginning of the intervention. This is considered continuing medical education, and we may be able to provide continuing medical education credit for their attendance. The training session will include information on prediabetes treatment guidelines, use of EPIC clinical decision support tools and use of the patient handout to discuss treatment options. There will be interactive skills practice incorporated. This training session may occur on up to 2 occasions to capture all PCPs. We may also record the training session so that PCPs who could not attend can view it later asynchronously.

Patients with prediabetes (e.g., “active” on prediabetes registry) presenting for a routine visit in the intervention clinic will be identified using an EPIC workbench report run the week prior to their upcoming visit. These patients, presenting for in-person or video visits, will receive the handout as an attachment either via MyChart or via email sent from REDCap.

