During the visit, the patients will be encouraged to bring the prediabetes handout to review with their PCP who can use the shared-decision making guide and treatment algorithm to discuss options with the patient. Several Epic clinical-decision support tools have been built to facilitate this discussion, including a prediabetes orders smartset (which includes the DPP referral) and prediabetes smart texts that PCPs can use to send patients information.

Patients who complete their visit will be invited via email (or MyChart if no email on file) to complete an online REDCap survey. They will first receive an email to complete the e-consent form which explains the study and the potential risk/benefits of joining the study. When the e-consent is completed, the patient will automatically receive a link to the survey. The survey is voluntary and will include up to 10 questions regarding their engagement in diabetes prevention behaviors and treatment, and satisfaction and acceptability of the intervention. The timing of the survey emails and reminders will be as follow: e-consent sent within 7 days of their visit and survey reminder 3 days after first invite. We will call patients who do not complete the e-consent form within 7 days of receipt and call patients who do not complete the survey within 5 days of receipt of the survey reminder. During the calls, we may offer to fill out the survey questions with the patient since our survey response rate has been low and this may increase uptake. Patients will be offered a \$10 gift card if they complete the survey. Regardless of whether patients fill out the survey, we will collect their medical record data using the PMAP database.

At the end of the visit, the patient will be encouraged to schedule a 3-6 month visit with their PCP or care team member to continue addressing prediabetes. At this follow-up visit, the same diabetes prevention clinical pathway steps will apply (i.e., handout sent before visit, survey to be completed after visit). The PCP or care team member will use the same shared-decision making guide and treatment algorithm to continue discussing treatment options with the patient.

Group 2 Control clinic patients

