Enrolled participants will be monitored throughout the study for untoward incidents (e.g., “Adverse Events”) occurring during the study. The Principal Investigator (and other designated individuals, if necessary) will conduct regular monitoring for safety concerns and provide general oversight for human subject safety requirements. Where necessary these occurrences will be evaluated for severity, attribution, and possible trends. All adverse events that are anticipated or described in the informed consent form will be logged appropriately and reported to the IRB on at least an annual basis (e.g., at continuing review).

Any Unanticipated Problems or unexpected “Serious Adverse Events” *related* to the study intervention or affecting the risk/benefit profile of the study, will be reported to the IRB promptly, and, in all cases, within 10 business days of discovery. Unplanned and non-emergent deviations from the IRB approved protocol will be logged and reported to the IRB annually at continuing review; all planned deviations will be submitted as a Change in Research to the IRB for approval and prior to implementation. All other event reporting requirements will be followed and all necessary parties will be notified of events/problems encountered in the study and/or changes in research, in accordance with all applicable regulations and guidelines.

Statistical Plan

Sample Size Determination and Power

We estimate that 1200 patients with prediabetes will be seen over the 12-month intervention period within each clinic (total sample of 2400 patients). Based on this sample, we estimate we will have 100% power to detect a change in rate of referral to DPPs from 0% to 25%. Additionally, we estimate that we will have 100% power to detect a change in documented prediabetes diagnosis from 10% (baseline rate estimated from Johns Hopkins data) to 34% (national estimate of the prevalence of prediabetes), follow-up lab testing completed from 50% (baseline rate estimated from Johns Hopkins data) to 60%, and referral to nutrition from 1% (baseline rate estimated from Johns Hopkins data) to 10%. In our analysis, we will assess the differences in trend of the outcomes in the baseline, intensive implementation, and sustainment periods.

Primary outcome variable

The primary outcome is whether patients with prediabetes are referred to a DPP and/or medical nutrition therapy and/or start metformin.

Secondary outcome variables

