The secondary outcomes are whether patients: 1) enroll in the DPP, 2) attend a medical nutrition therapy visit, 3) complete follow-up glycemic testing, 4) fill metformin, 5) achieve weight loss $\geq 5\%$ and 6) complete PCP/team follow-up visit.

Other process outcomes we will look at include whether MyChart messages with the prediabetes handout are read.

Statistical Methods

For the analysis, we will include patients with prediabetes (identified by prediabetes registry) who have completed at least once PCP visit during the first 6 months of the 12-month intervention period. We will compare the primary outcomes and other secondary outcomes between the intervention and control clinics.

We will conduct an interrupted time series analysis to evaluate the differences in trend of the outcomes in the baseline (V0-12m), intensive implementation (T0-T6m), and sustainment periods (T6m-T12m) at the patient level. We will compare these outcomes in the pre- and post-intervention periods using logistic regression models with generalized estimating equations to account for repeated observations within patients. We will use multivariate logistic regression models to determine predictors of these outcomes adjusting for race, age, and baseline HbA1c. We may adjust for clinic-level characteristics, such as patient safety culture using GLINT survey data from 2021 and 2022 if available. We will only request aggregate data from the clinic-level on safety culture.

Study Administration

Funding Source

Funding for this study is provided by the National Institute of Diabetes and Digestive Kidney Diseases under Award Number K23DK118205 (PI: [name]).

Subject Stipends and Payments

Patients who complete the survey will receive a \$10 gift card, either mailed to their home address or sent as an e-gift card based on patient preference. The last survey question will ask them to provide this information, which will not be linked to other responses. Clinicians who

complete the survey will get a \$25 e-gift card sent to the email address they provide. Again, their response to this question will not be linked to other responses.

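### The power statement for follow-up testing starts from 50%, but the Johns Hopkins cohort reported in the same document had 63.4%, and the 60% target lies below that

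*Combined protocol and SAP*

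**What the plan says.** **Statistical Plan, Sample Size Determination and Power.** The plan expects 1200 patients per clinic: "We estimate that 1200 patients with prediabetes will be seen over the 12-month intervention period within each clinic (total sample of 2400 patients". On that basis it claims 100% power for several changes, among them "follow-up lab testing completed from 50% (baseline rate estimated from Johns Hopkins data) to 60" per cent. Two further baselines carry the same Johns Hopkins attribution: documented diagnosis at 10% and nutrition referral at 1%.

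**Introduction, Purpose of the Study Protocol.** The sponsor's retrospective Johns Hopkins cohort is summarised in one sentence: "Within 12 months, 63.4% had repeat glycemic testing, yet only 10.4% had coded diagnoses of prediabetes, 1.0% were referred for nutrition services".

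**Secondary outcome variables.** Testing is listed as "3) complete follow-up glycemic testing", with no time window.

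**Statistical Methods.** The analysis covers patients with a PCP visit in the first 6 months of the intervention period. Trends are compared across "baseline (V0-12m), intensive implementation (T0-T6m), and sustainment periods (T6m-T12m) at the patient level".

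**The concern.** The plan gives two rates for what appears to be the same care activity, both attributed to Johns Hopkins, and they differ by more than rounding could produce. The sample-size section has three baselines labelled as Johns Hopkins data. Two equal the cohort figures in the Introduction once rounded; only testing does not. No sentence gives the 50% a different source, population, test definition or time window.

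What is at stake is the meaning of one power claim. Testing is a named secondary outcome with its own power statement. If usual care already reaches 63.4% over the window analysed, a target of 60% would be a decline, and power to detect a move from 50% to 60% tells the reader nothing about the chance of showing a benefit.

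**Working it through.** **Inputs**

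| Quantity | Value | Where |
|---|---|---|
| Testing, planning baseline and target | 50%, 60% | Sample Size Determination and Power |
| Testing, cohort, 12 months | 63.4% | Purpose of the Study Protocol |
| Patients per clinic | 1200 | Sample Size Determination and Power |
| Significance level | two-sided 5% | assumed; not stated |
| Patients independent | yes | assumed, for a simple two-clinic comparison |
| Analysed number below 1200 | 900 or 600 per clinic | assumed, for illustration |

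**Step 1. Compare the three baselines attributed to Johns Hopkins**

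| Item | Cohort (Introduction) | Power section | Difference (points) |
|---|---|---|---|
| Coded or documented diagnosis | 10.4% | 10% | 0.4 |
| Nutrition referral | 1.0% | 1% | 0 |
| Repeat or follow-up testing | 63.4% | 50% | 13.4 |

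The first two differences are rounding. The third is not. Target minus cohort rate: 60 − 63.4 = −3.4 points.

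**Step 2. Reproduce the plan's own figure**

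Pooled-variance normal approximation, equal groups of n, with p̄ = (p1 + p2)/2:

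- SE0 = √[2p̄(1 − p̄)/n]
- SE1 = √{[p1(1 − p1) + p2(1 − p2)]/n}
- power = Φ[(|p2 − p1| − 1.96·SE0)/SE1]

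For 50% to 60% at n = 1200:

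- p̄ = 0.55
- SE0 = √(2 × 0.55 × 0.45/1200) = 0.02031
- SE1 = √[(0.25 + 0.24)/1200] = 0.02021
- z = (0.10 − 1.96 × 0.02031)/0.02021 = 2.98
- power = 99.86%

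This rounds to the stated 100%. A continuity correction gives 99.83%, so the result does not depend on that choice.

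**Step 3. Start from the cohort rate instead**

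For 63.4% to 73.4% at n = 1200:

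- p̄ = 0.684
- SE0 = 0.01898
- SE1 = 0.01887
- z = (0.10 − 1.96 × 0.01898)/0.01887 = 3.33
- power = 99.96%

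For a 5-point gain, 63.4% to 68.4%, at n = 1200:

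- SE0 = 0.01935
- SE1 = 0.01933
- z = (0.05 − 1.96 × 0.01935)/0.01933 = 0.62
- power = 73.4%

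By the same formula, the smallest gain from 63.4% that is detectable at n = 1200 is about 5.4 points for 80% power and 6.2 points for 90% power.

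**Step 4. Allow for the number analysed**

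The 1200 are patients seen over 12 months, whereas Statistical Methods keeps only those with a visit in the first 6 months. The plan does not say how many that will be.

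| Analysed per clinic | Power, 63.4% to 73.4% |
|---|---|
| 1200 | 99.96% |
| 900 (assumed) | 99.6% |
| 600 (assumed) | 96.2% |

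**The case against.** The strongest reply is that no contradiction has been proved. The sample-size section does not say that its Johns Hopkins data are the cohort in the Introduction. It speaks of completed follow-up laboratory tests rather than repeat glycemic tests, and it gives no window, whereas 63.4% is a 12-month figure. A shorter window would give a lower rate, and the plan contains shorter ones: a visit at 3 to 9 months ("patients will be scheduled for a follow-up visit within 3-9 months with their PCP or care team (NP"), a visit at 3 to 6 months ("the patient will be encouraged to schedule a 3-6 month visit with their PCP or care team member"), and two 6-month analysis phases. So 50% may have a legitimate origin. Putting 63.4% in its place without checking the window could create a new mismatch.

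Much of this stands. A reader might infer that 50% is simply wrong, or that the trial is certainly aiming below usual care. The documents support neither reading, because nothing says whether 63.4% applies to these clinics over the period analysed. A reader might also infer that the power calculation is faulty or that the trial is underpowered for testing. Step 2 shows that the calculation reproduces, and Step 3 that a 10-point gain keeps nearly the same power from either baseline.

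The reply does not remove the inconsistency. The plan ties the 50% to none of those windows, and the agreement of the other two baselines with the cohort makes a shared source the natural reading.

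**Conclusion.** The point holds as a minor inconsistency in one planning input. Two testing rates attributed to Johns Hopkins differ by 13.4 points without explanation, and the 60% target is 3.4 points below the higher one. Confidence is high for that mismatch only.

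The consequence, that the power claim describes no improvement, holds only if the 63.4% applies to the outcome as analysed, which the documents neither confirm nor exclude. The recomputed power figures rest on a two-sided 5% test and independent patients; those at 900 and 600 per clinic also rest on assumed numbers.

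The primary outcome (referral to a DPP or to nutrition therapy, or starting metformin) does not include testing and is not affected. Nor is the estimate of 2400 patients, which is a count of those expected to be seen and was not derived from the testing contrast.

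**What to change.** In Sample Size Determination and Power, reconcile the testing baseline with the Introduction:

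1. State the window over which follow-up testing is analysed.
2. Use the 63.4% cohort rate, expressed over that window, with a target above it. If the analysed window is not 12 months, take the cohort rate for the matching window.
3. Restate power at the number actually analysed under Statistical Methods. If the plan's 10-point gain is kept over 12 months (63.4% to 73.4%), the Step 4 values apply. If a gain near 5 points is what is expected, power is well short of 100% even at 1200 per clinic, and the actual figure should be given.
4. Keep 50% only if it comes from a different source, window or definition that matches the analysed outcome, and say so in the same sentence.

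The cost is one clause in the power section, plus a look-up of where the 50% came from and a count of the patients expected in the first 6 months. The primary outcome, the data collected and the recruitment estimate need no change.

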Patients with prediabetes (e.g., “active” on prediabetes registry) who present for a routine visit in the control clinic will be identified using an Epic workbench report. Their PCP will address prediabetes as they usually do (i.e. usual care). They can refer patients to the same interventions (DPP, MNT) or start metformin. PCPs will have access to the same Epic clinical-decision support tools as the intervention clinic does but not the shared-decision making guide and treatment algorithm to facilitate discussion. Patients will not receive the prediabetes handout.

Patients who complete their visit will be invited via email to complete an online REDCAP survey. They will first receive an email to complete the e-consent form which explains the study and the potential risk/benefits of joining the study. When the e-consent is completed, the patient will automatically receive a link to the survey. The survey is voluntary and will include up to 10 questions regarding their engagement in diabetes prevention behaviors and treatment, and satisfaction with prediabetes care. The timing of the survey emails and reminders will be as follow: e-consent sent within 7 days of their visit and survey reminder 3 days after first invite. We will call patients who do not complete the e-consent form within 7 days of receipt and call patients who do not complete the survey within 5 days of receipt of the survey reminder. During the calls, we may offer to fill out the survey questions with the patient since our survey response rate has been low and this may increase uptake. Patients will be offered a \$10 gift card if they complete the survey. Regardless of whether patients fill out the survey, we will collect their medical record data using the PMAP database.

Group 3 Intervention clinic PCPs

PCPs in the intervention clinic will be recruited to provide feedback using an online REDCap survey through an in-depth survey sent via email at 0m, 6m and 12m to gather feedback on intervention components and acceptability/satisfaction with the intervention. PCPs will receive an email from REDCap with the e-consent form. Once that is completed, the PCP will receive the survey link. All survey participants will receive a \$25 gift card for completion of the in-depth survey.

Safety and Adverse Events

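### Weight enters the analysis only as a yes/no at 5% loss; a continuous percent-change analysis of the same weights should be added beside it (minor).

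*Combined protocol and SAP*

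**What the plan says.** The section Secondary outcome variables frames all six outcomes as yes/no: "The secondary outcomes are whether patients: 1) enroll in the DPP", and so on. The fifth is "5) achieve weight loss" of at least 5%. Weight is mentioned as an outcome nowhere else.

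Statistical Methods compares the pre- and post-intervention periods "using logistic regression models with generalized estimating equations to account for repeated observations within patients", and adds "multivariate logistic regression models to determine predictors of these outcomes adjusting for race, age, and baseline HbA1c". No linear model, mean change or other continuous outcome is named, and baseline weight is not among the listed adjusters. No reference weight or follow-up window is stated for the 5% criterion.

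On data, the Group 1 and Group 2 descriptions both say that, whether or not a patient fills out the survey, "we will collect their medical record data using the PMAP database". Weight is not named as an extracted item, but a 5% loss cannot be scored without at least two weights per patient.

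Sample Size Determination and Power covers DPP referral, documented diagnosis, follow-up testing and nutrition referral. It gives no power, SD, responder rate or target difference for weight.

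**The concern.** A cut at 5% gives the same score to a patient who loses 4.9% and one who gains 5%, and small errors in routine weights move patients near the cut from one category to the other. The other listed outcomes are care processes or use of services, so weight is the plan's only physiological outcome.

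The pathway consists of clinician training, a handout, a decision guide and referral, while control clinicians can make the same referrals, start metformin and use the same Epic tools. Any effect on weight must pass through referral, attendance and adherence, so a modest mean difference is plausible. A threshold outcome is least efficient for that kind of effect. What is at stake is the reading of one secondary outcome in a pilot that is meant to inform system-wide implementation.

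**Working it through.** **Inputs from the documents.** 1200 patients per clinic, 2400 in total (Sample Size Determination and Power). The analysis set is restricted to patients "who have completed at least once PCP visit during the first 6 months of the 12-month intervention period" (Statistical Methods); its size is not given. Video visits count as qualifying visits (Study Design).

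**Assumptions, because the documents are silent.** Two-sided alpha 0.05; percent weight change normal; SD 5 to 7 points; mean control loss 0 to 2% for the information figures and 0 to 1% for power; the same shift in every intervention patient; independent patients. The figure of 600 per clinic is also assumed, to show what happens if the six-month restriction and missing weights halve the number.

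**The plan's own figures.** At 1200 per clinic, a two-proportion comparison gives 100% (0 v 25%), 100% (10 v 34%), 99.9% (50 v 60%) and 100% (1 v 10%). The stated 100% is reproduced. None of the four concerns weight.

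**Information kept by the cut.** For a small common shift, the fraction kept is φ(z)² / [p(1 − p)], where p is the share reaching 5% and z the matching normal quantile, z = (5 − mean) / SD.

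- p = 50%: 0.3989² / 0.25 = 0.637, so 36% is lost.
- p = 25%: 0.3178² / 0.1875 = 0.539, so 46% is lost.
- p = 10%: 0.1755² / 0.09 = 0.342, so 66% is lost.
- Mean loss 0, SD 5: z = 1.00, p = 0.159, kept 0.439, so 56% is lost.
- Mean loss 2, SD 7: z = 0.429, p = 0.334, kept 0.595, so 40% is lost.

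**Power for a 1-point mean difference, SD 6, control loss 1%.** The shares reaching 5% are P(Z > 4/6) = 0.2525 and P(Z > 3/6) = 0.3085, a difference of 0.0561.

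- Continuous, 1200 per clinic: SE = 6 × √(2/1200) = 0.245; 1/0.245 − 1.96 = 2.12; power 98%.
- Binary, 1200 per clinic: pooled SE 0.01834, unpooled SE 0.01831; (0.0561 − 1.96 × 0.01834) / 0.01831 = 1.10; power 86%.
- 600 per clinic (assumed): 82% continuous, 58% binary.
- Patients per clinic for 80% power: 566 continuous, 1008 binary.

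**Sensitivity, over SD 5 to 7 and control loss 0 to 1%.**

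| True difference | Per clinic | Binary | Continuous |
|---|---|---|---|
| 1.0 point | 1200 | 73–95% | 94–99.8% |
| 1.0 point | 600 | 45–71% | 70–93% |
| 1.5 points | 1200 | at least 97% | at least 99.9% |

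**If the effect is concentrated.** Suppose the 1-point mean difference comes from 25% of intervention patients who each lose 4 points more (SD 6, control loss 1%). The intervention share reaching 5% is 0.75 × 0.2525 + 0.25 × 0.50 = 0.314, and the intervention SD rises to √(36 + 0.25 × 0.75 × 16) = 6.24. Power is then 92% binary v 98% continuous at 1200, and 66% v 81% at 600. The gap narrows but does not close.

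**The case against.** A prespecified 5% responder outcome is legitimate and easy to read clinically, and choosing it is not an error. Weight is one of six secondary outcomes in a pilot whose primary outcome is referral or metformin start. All of this stands, and it is why the point is minor and why the 5% outcome should stay.

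The size of the loss is not a property of the documents. A reader might infer that the plan throws away about half the information as a matter of fact. The documents give neither the responder share nor the distribution on which that depends: a loss of 40 to 55% needs normal weight change and roughly 17 to 34% of patients reaching 5%. A common shift also favours the continuous analysis. The pathway works partly through referral, with 25% DPP referral as the powered target, so a concentrated effect is credible and the loss is then smaller. Heavy tails act in the same direction: with t-distributed change on 3 to 5 degrees of freedom (SD 6, control loss 1%), the cut keeps 62 to 67%. Outlying routine weights would also trouble a linear model.

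The power figures compare independent patients. The trial is non-randomised, has one clinic per arm and plans a pre/post analysis. Clinic differences limit any weight comparison, and a continuous outcome does not remove them.

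What survives is that, in every scenario examined, the continuous analysis is the more powerful, and the weights have to be obtained anyway.

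**Conclusion.** The point holds as a minor one. The plan analyses weight only as a yes/no at 5%, and a more powerful analysis of the same measurements is left out. Under normality with a common shift the loss runs from 36% (half the patients reaching 5%) to 66% (one in ten), or 40 to 56% if mean loss is 0 to 2% and SD 5 to 7 points. It is smaller if the benefit falls on a minority.

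A reader might go further and infer that the trial is likely to report no weight effect when there is one. The documents do not support that. At the planned 1200 per clinic a difference of 1.5 points or more is detected either way, and a 1-point difference still has about 86% binary power in the central scenario. The exposure is to differences of about 1 point or less, or to a marked fall in the number with usable weights. Such a fall is possible, since only patients seen in the first six months are analysed and video visits may lack a weight, but the documents give no number for it.

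**What to change.** Keep the at-least-5% outcome and its logistic analysis as planned. Add percent weight change from baseline as a continuous secondary analysis, using a linear repeated-measures model (GEE or mixed) with clinic, period, clinic-by-period and baseline weight.

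Prespecify one baseline weight definition and one follow-up window, identical in both clinics, and derive the 5% share from the same weights. The window matters because the pathway prompts follow-up visits in the intervention clinic; if every recorded weight counted, those extra visits would help decide which weights enter the comparison. Report the number with usable weights in each clinic.

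The cost is one extra model and a few lines of SAP text, with no new patient contact. The small downside is that the mean difference has to be read beside the 5% share to be clinically interpretable. The change does nothing for the one-clinic-per-arm limitation, which should be stated with the result.
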